#### Choices of bupropion and fluoxetine for the treatment:

Bupropion is unique amongst antidepressants because it selectively blocks reuptake of NE and DA without having appreciable affinity for postsynaptic receptors including histamine, α- or β-adrenergic, 5-HT, or acetylcholine [30, 88]. This confers a favorable side effect and safety profile [89], absence of weight gain [90] or somnolence [91]; side effects frequently reported by HD patients with other antidepressants [92-95]. Bupropion has no clinically significant effects on the cardiovascular system (e.g., heart rate, blood pressure, QTc interval) in patients with MDD [96]. It can increase the incidence of seizures [97] in a dose-dependent (>450 mg/day) [30] fashion in patients with a history of seizures; therefore it is contraindicated in these patients. Bupropion may preferentially reduce a subset of symptoms of MDD common in medically ill patients, including fatigue, drowsiness, cognitive dysfunction, anhedonia, and mental concentration [98, 99]. In healthy humans, after oral administration, bupropion is rapidly and ~100% absorbed by the intestine, metabolized in the liver, and excreted via kidney. The hepatic cytochrome P450 (CYP) 2B6 catalyzes bupropion to a primary active metabolite, hydroxylbupropion. Several studies [62, 100, 101] have provided guidelines and recommendations about antidepressant agents in patients with ESRD/HD. One study [80] determined the PK of bupropion and its active metabolites in HD patients following a single 150-mg oral dose and found comparable PK profile to individuals with normal renal function. Compared with controls, hydroxyl-bupropion demonstrated a >2fold greater AUC and substantially increased t1/2, indicating reduced clearance. Based on these data, the authors [80] suggested an oral dose of 150 mg bupropion every 3 days in HD patients.

While it has been suggested that antidepressants may in general reduce inflammation, research data suggests that SSRIs and tricyclic antidepressants may not. Other hand, there has been considerable recent interest in the anti-inflammatory effects of bupropion, although more research is needed [102]. Brustolim et al. [33] demonstrated that bupropion significantly reduced the levels of TNF- $\alpha$  in mice challenged with lipopolysaccharide and suggested that this effect might have important clinical consequences. In case reports, Kast and Altschuler [35, 36] proposed the potential anti-inflammatory

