#### For patients on HD

- have patent and non-infected arteriovenous fistula or graft;
- are receiving maintenance HD 2-3 times per week;

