Participation of an eligible subject in this clinical trial is a voluntary process. Subjects will not be coerced or influenced by the study personnel. In order to participate, subjects will have to voluntarily initiate a phone screening and subsequently come to a face-to-face consent/initial evaluation meeting. A research staff member or study investigator will conduct the consent process in order to minimize the possibility of undue influence from the treating physician on their hemodialysis team. Subjects will be informed that participation is voluntary and not participating will not affect the delivery of the routine health care. They and their treating physicians will be informed that the medications being used in the current study are routinely available and relatively inexpensive to obtain. They do not have to participate in this study to receive any of the treatment options.

Subjects are randomly assigned to open label treatment with one of two medications. Therefore, there are two groups:

- Bupropion group:
  - For patient not on hemodialysis, oral administration of bupropion SR tablet at a dose of 150 mg daily. Bupropion SR doses will be adjusted upward or downward based on tolerability and response.
  - For patient on hemodialysis or peritoneal dialysis, oral administration of bupropion SR tablet at a dose of 150 mg on the 1st and the 3rd dialysis day of each week. Bupropion SR doses will be adjusted upward or downward based on tolerability and response.
- Fluoxetine group: Oral administration of fluoxetine tablet will be started at a dose of 10 mg/day for the first week and then increased, as tolerated to 20 mg/day for weeks 2–4. After this, doses will be adjusted based on clinical response and side effects up to a maximum dose of 60 mg/daily by week 10.

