## 6. Research Plan

The current study proposes to recruit up to 50 participants in order to have 40 completers. Eligible CKD patients with MDD will be randomly assigned to 12 weeks of open label, flexible dose treatment with either Bupropion SR (N=20) or Fluoxetine (N=20). Patients will be recruited from the UAMS dialysis center or other local dialysis centers via flyers, referral by their treating physician and/or newspaper ads. Written consent will be obtained before any study procedures. Subjects are randomly assigned to open label treatment with one of the following:

• Bupropion group:

Version #: 17, IRB #203076

PI: [name]

 For patient not on hemodialysis or peritoneal, oral administration of bupropion SR tablet at a dose of 150 mg daily. Bupropion SR doses will be adjusted upward or downward based on tolerability and response.

- For patient on hemodialysis or peritoneal dialysis, oral administration of bupropion SR tablet at a dose of 150 mg on the 1st and the 3rd dialysis day of each week. Bupropion SR doses will be adjusted upward or downward based on tolerability and response.
- Fluoxetine group: Oral administration of fluoxetine tablet will be started at a dose of 10 mg/day for the
  first week and then increased, as tolerated to 20 mg/day for weeks 2–4. After this, doses will be
  adjusted based on clinical response and side effects up to a maximum dose of 60 mg/daily by week
  10.

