Participants will receive the study medication during the baseline assessment and instructed to begin the medication on day 1 (1st dialysis day) of week 1 of the study. For patient on hemodialysis or peritoneal dialysis, generic bupropion SR will be dosed at 150 mg on the 1st and the 3rd dialysis day of each week with doses adjusted upward or downward based on tolerability. The initial dose of bupropion-SR is based on the findings of Worrall et al [80], who measured plasma bupropion levels in a pharmacokinetic study of bupropion in HD patients. For patient not on hemodialysis or peritoneal dialysis, generic bupropion SR tablet will be dosed at 150 mg daily. Bupropion SR doses will be adjusted upward or downward based on tolerability and response. Fluoxetine will be started at 10 mg/day for the first week and then increased, as tolerated to 20 mg/day for weeks 2–4. After this, doses will be adjusted based on clinical response and side effects up to a maximum dose of 60 mg/daily by week 10 [62]. At the week 12 visit, the participants will stop the medication or may undergo a 1-2 week taper (depending on maintenance dose) if they are on a dose of fluoxetine that is higher than 20 mg.

Subjects will be seen during weeks 1, 2, 3, 4, 6, 8, 10, and 12 in face-to-face meetings by a rater blind to study medication and a study physician for Ham-D ratings, CGI, medication accountability, and measurement of adverse events. On weeks 5, 7, 9 and 11, subjects will come in to return the previous week's pill bottles and pick up the current week's medication. Table 1 shows study procedures. Medication will be prepared by UAMS Research Pharmacy, labeled with the directions for use and contact information, and given to participants by study staff on a weekly basis. Compliance will be monitored using the MAFV at each scheduled encounter and by analysis of antidepressant blood levels. Results of a second EKG done during week 4 will be reviewed to ensure QTc interval is less than 500 msec.

In order to control for the potential confound of chronic pain we will characterize it with the physical and psychological pain scale and with two objective measures, i.e. the pressure pain threshold and the Quantitative Sensory Test (QST).

Version #: 17, IRB #203076

PI: [name]

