#### Study Intervention #1 Benefits Bupropion SR Group Bupropion SR Group Possible improvement in depression status Reasonably foreseeable risks: **Not serious** Serious Dizziness None These risks are expected to occur Agitation in more than 10 out of 100 Blurred vision subjects. Tremor Sweating Headache/migraine Inability to get adequate sleep Increased heart beat Dry mouth Constipation Decreased appetite Nausea, vomiting Weight gain **Serious Not serious** Less likely High blood pressure (Hypertension) Abnormal heart rhythm These risks are expected to occur Low blood pressure (Hypotension) in 2-9 subjects or less out of 100 Skin rash and itching subjects. Impotence Urinary frequency **Arthritis** Slowness in movement (bradykinesia) Upper respiratory complaints Fatigue Anxiety Decreased sexual desire (libido) **Serious** Rare These risks are expected to Urinary retention 1) Suicidal ideation occur in less than 1 subject in 100. 2) Suicide 3) Faint (syncope) 4) Seizures. In doses over 400mg per day, bupropion SR can be associated with seizures. The incidence of seizure with bupropion SR at the usual daily dose of 300 mg is approximately 0.1%, (or 1 out of 1000 patients), increases to approximately 0.4% at the maximum dose of 400 mg/day. The dose of 150 mg twice per week used in this study was previously shown to lead to blood levels in hemodialysis patients comparable to those obtained during routine treatment of non-hemodialysis patients treated with 300 mg daily.

Version #: 17, IRB #203076

PI: [name]

Study Intervention #2 Benefits							
Fluoxetine Group							
Fluoxetine group	Possible im	provement in depression status					
Reasonably foreseeable risks :							
	Not serious		Serious				
Likely These risks are expected to occur in more than 10 out of 100 subjects.	

Decreased app

Anxiety

Nervousness

Inability to obtasleep (insomni

	ain adequate	• None				
	Not serious		Serious				
Less likely These risks are expected to occur in 2-9 subjects or less out of 100 subjects.	• Impaired	thinking	

Alteration in blood glucose

Abnormal bleeding

Weight loss

				
			Serious				

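### The bupropion starting rule for dialysis patients names a third dialysis day that twice-weekly hemodialysis patients do not have, so it does not deliver the stated dose of 150 mg twice a week

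*Combined protocol and SAP*

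**What the plan says.** The eligibility criteria in Section 4, under the heading for patients on HD, admit those who "are receiving maintenance HD 2-3 times per week". Both two-session and three-session schedules therefore qualify.

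The bupropion starting dose for dialysis patients appears three times with the same day rule: in the treatment-group bullets of Section 5, in the bullets of Section 6 ("oral administration of bupropion SR tablet at a dose of 150 mg on the 1st and the 3rd dialysis day of each week") and in the later narrative of Section 6 ("generic bupropion SR will be dosed at 150 mg on the 1st and the 3rd dialysis day of each week"). None of the three has a separate line for a patient with two sessions a week.

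Two other places show what dose was intended. The bupropion table under Risks and Benefits states: "The dose of 150 mg twice per week used in this study was previously shown to lead to blood levels in hemodialysis patients", and goes on to liken those levels to the ones seen with 300 mg daily outside hemodialysis. The background section on the choice of drugs reports that the authors of a pharmacokinetic study in hemodialysis patients "suggested an oral dose of 150 mg bupropion every 3 days in HD patients". Section 6 cites that same study when it says "The initial dose of bupropion-SR is based on the findings of" its authors.

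**The concern.** The day rule works for one of the two hemodialysis schedules that the protocol accepts and fails for the other. Staff who follow it literally would start a twice-weekly patient on one tablet a week. Staff who see the problem must choose the second day themselves, and different staff may choose differently.

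At stake is whether every dialysis patient in the bupropion arm starts on the dose that the protocol says is being studied. The risk table's blood-level comparison is stated for 150 mg twice a week. Nothing in the documents extends it to once a week.

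**Working it through.** The check is a count of scheduled tablets under the rule as written.

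**Inputs**
- Tablet strength: 150 mg (Sections 5 and 6).
- Dosing days: dialysis days 1 and 3 of each week (Sections 5 and 6).
- Eligible hemodialysis sessions per week, *s*: 2 or 3 (Section 4, patients on HD).
- Stated study dose: 150 mg twice a week (Risks and Benefits, bupropion table).
- Dose suggested by the cited pharmacokinetic study: 150 mg every 3 days (background section on the choice of drugs).

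**Formula.** Weekly dose = 150 mg × (number of days in {1, 3} that do not exceed *s*).

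**Three sessions a week.** Days 1 and 3 both exist: 2 × 150 = 300 mg a week. The stated dose is 2 × 150 = 300 mg a week, so the plan's own figure is reproduced.

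**Two sessions a week.** Only day 1 exists: 1 × 150 = 150 mg a week. Against the stated dose, 150 / 300 = 50%. The plan's figure is not reproduced.

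**Cross-check on intent.** Every 3 days averages 150 × 7/3 = 350 mg a week. That is the cited authors' suggestion and not the dose the protocol adopted, so the comparison that measures the inconsistency is 150 against 300. It does confirm that the source points to about two tablets a week and not one.

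**Effect on the arm, by assumption.** The documents do not give the share of twice-weekly patients. If a fraction *p* of the bupropion hemodialysis patients is on two sessions and the rule is followed literally, their mean starting dose is 300 − 150*p* mg a week:

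| Assumed *p* | Mean starting dose (mg/week) |
|---|---|
| 0 | 300 |
| 0.10 | 285 |
| 0.25 | 262.5 |
| 0.50 | 225 |

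**After the change.** With two sessions and a tablet on each dialysis day, 2 × 150 = 300 mg a week, which matches the risk table.

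**The case against.** The strongest reply is that the rule does not order half a dose. Where a third dialysis day does not exist, the instruction is undefined, and the risk table supplies the answer of two tablets a week. On that reading only the day of the second tablet is missing. This is fair, and it is why the point is put as one tablet or an undefined second one. It does not remove the need for a change, because none of the three places that set the dose states the twice-weekly figure.

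A second reply is that this is only a starting dose in a flexible-dose trial. The bullets in Sections 5 and 6 allow adjustment for tolerability and response. A study physician sees patients in weeks 1, 2, 3, 4, 6, 8, 10 and 12, medication is dispensed weekly with written directions, and drug levels are taken at weeks 4 and 12. A literal misreading would also lower exposure, in patients for whom the protocol reports reduced metabolite clearance. All of this stands and limits the consequence. One reservation remains: the Section 6 narrative ties adjustment of the dialysis dose to tolerability alone, and no step size or timing is given for bupropion.

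Three stronger inferences might tempt a reader, and the documents do not support them.
- *Peritoneal dialysis patients are assigned daily dosing.* The Section 5 bullet ("For patient not on hemodialysis, oral administration of bupropion SR tablet at a dose of 150 mg daily") does not exclude them, but the next bullet places them on the dialysis regimen. The corresponding Section 6 bullet ("For patient not on hemodialysis or peritoneal, oral administration of bupropion SR tablet at a dose of 150 mg daily") and the narrative agree. This is loose wording, already resolved.
- *The weekly pill count loses its reference.* The medication accountability text describes recording the missing pills and sets no number due. Under flexible dosing, that number depends on each patient's current directions in any case.
- *The risk table contradicts the daily regimen for non-dialysis patients because it does not repeat it.* Its sentence concerns blood levels in hemodialysis patients, and Sections 5 and 6 give the non-dialysis dose.

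**Conclusion.** The concern holds in a narrow form. Section 4 admits a two-session schedule for which the dosing rule in Sections 5 and 6 yields one 150 mg tablet a week or leaves the second unspecified, against a stated study dose of 300 mg a week. On the literal reading the shortfall is 50% of the intended starting dose.

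This rests on two assumptions: that the risk table states the intended dose, which the every-3-days source supports, and that no operational document outside the protocol already names the days.

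The scope is twice-weekly hemodialysis patients in the bupropion arm (planned N = 20, shared among non-dialysis, hemodialysis and peritoneal patients). Their number is not given and may be zero. A reader might infer that these patients would be under-treated throughout the 12 weeks, or that the treatment comparison would be biased. The documents do not support either: titration can correct the dose, and the number affected cannot be sized. No power, sample-size or analysis figure depends on this. Severity is minor.

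**What to change.** In the bullets of Section 5, the bullets of Section 6 and the Section 6 narrative, replace the dialysis rule with: *Patients on dialysis start at 150 mg twice per week: on the 1st and 3rd dialysis day if hemodialysis is three times a week, and on both dialysis days if hemodialysis is twice a week.* Keep the existing provision for adjustment.

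The same amendment can tidy two related phrases. Name two fixed days of the week for peritoneal dialysis patients, for whom a dialysis day is not defined. Also make the daily-dose bullets in Sections 5 and 6 read *not on hemodialysis or peritoneal dialysis*.

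The cost is a wording amendment to Sections 5 and 6. Design, sample size, visits and analysis stay as they are.

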# **4. Study population** is defined as CKD patients with chronic kidney disease with MDD. **Inclusion Criteria**

- age 30-70 vrs:
- meet the Diagnostic and Statistical Manual of Mental Disorders, 4th Edition (DSM-IV) criteria for MDD;
- have a Ham-D score > 17
- if receiving any of these medications, on a stable or maintenance dose of iron or erythropoietinstimulating agents, statins, angiotension receptor blockers and/or angiotension converting enzyme inhibitors, phosphate binders and vitamin D receptor analogs as these agents may influence cytokines proposed in the study;
- serum albumin of ≥ 3.2 g/dl, serum phosphate of <6.5 mg/dl, and serum hemoglobin of ≥9 mg/dl in two consecutive blood tests [subjects failing screening due to these blood tests will be allowed to be re-screened in 30 days];

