#### **Exclusion Criteria**

- meet DSM-IV criteria for Bipolar Disorder or other psychotic disorder in the month prior to screening:
- are taking antidepressants, anti-anxiety medications, or hypnotics (including Zyban for smoking cessation);

Version #: 17, IRB #203076

PI: [name]

- failure to respond to or tolerate bupropion or fluoxetine in the past
- allergic to fluoxetine or bupropion
- known history of HIV/AIDS; No testing will be conducted for screening purposes
- known history of alcohol or drug abuse or dependence within the month prior to screening based on clinical records;
- history of myocardial infarction or heart failure within one month of screening or a history of seizures or stroke at any point;
- history of chronic liver disease and diagnosis of hepatic encephalopathy based on clinical records;
- · currently diagnosed with cancer or receiving any cancer treatment;
- history of any infection within the last 2 weeks;
- currently taking any antibiotics, anti-inflammatory (low dose aspirin is acceptable), and immune-modulator agents;
- recorded noncompliance with dialysis schedules; and
- currently participating in clinical or behavioral intervention studies.

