After consent, subjects will be interviewed by a study staff for eligibility, including a review of medical records (if available), clinical interview, physical examination, routine blood tests, and EKG, if not already available (within one month). Psychiatric diagnosis will be established after interview using the Mini International Neuropsychiatric Interview (MINI) [75], depressive symptoms will be assessed with the Hamilton Depression (HAM-D) Scale [76], and cognitive status will be assessed using the n-back and MSIT tasks [77] and the Modified Mini Mental Status (3MS) Examination [78]. Pain will be characterized with the Physical and Psychological Pain Scale [142]. Pressure pain threshold will be measured with an Algometer [143]. Thermal pain sensitivity will be characterized with Quantitative Sensory Testing (QST). Delay discounting, MSIT and n-back will be the primary measures of cognitive function and the 3MS will be used for comparison to other studies. History of prior antidepressant treatment and response will be obtained using the Antidepressant Treatment Response Questionnaire (ATRQ) [79]. Given the underrecognized role of dental and gum disease in systemic inflammation a basic noninvasive dental evaluation will be performed by [name] at UAMS Dental Hygiene Clinic. Dialysis dose, pre- and post-dialysis body weight and blood pressure, serum urea nitrogen, albumin, serum phosphate hemoglobin, calcium, parathyroid hormone, vitamin D and lipid profile will be extracted. Measures of dialysis adequacy (kt/V) will also be extracted.

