#### **Procedures to Minimize Risks**

- All side effects will be closely monitored;
- Physical examination and blood test results will be performed reviewed to help detect an increased risk of developing side effects;
- Aseptic precautions to minimize risks associated with blood draw;
- Subjects will be educated to share any unusual event or change in their health with the study staff;
- Study staff will ask questions to elicit any new event or change in their health during each encounter;
- The study procedures to be performed on subjects are consistent with sound research design.
- Participants maintained on fluoxetine at doses higher than 20 mg/day will undergo a 1-2 weeks taper depending on the maintenance dose.
- The researchers have taken steps to minimize the known or expected risks. However, appropriate medical treatment will be provided for any adverse event (anticipated or un-anticipated) as per standard medical practice and guidelines. In addition, the event will be documented for proper notification. In addition, following measures will be implemented:
  - All patients will continue to be managed by their treating physician during the study. Acute events that may require hospitalization for reasons unrelated to the study are possible in this population. These events and possible interruptions of study drugs will be recorded, and if necessary, patients may be discontinued from the study. Patients expressing suicidal ideation or plans will be brought to the attention of the treating physician and treatment options discussed. The PI will be available for consultation on such cases. Depending on the severity and/or wishes of the treating

Version #: 17, IRB #203076

PI: [name]

physician and patient, a number of options are available, including transportation to an emergency department medical facility, referral to Psychiatry outpatient clinic, or medical intervention at a nearby dialysis center.

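### The protocol's only QTc limit (below 500 msec) first applies at week 4; no written rule applies it to the EKG taken before treatment

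*Combined protocol and SAP*

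**What the plan says.** The eligibility work-up in Section 6 (Research Plan) includes "routine blood tests, and EKG, if not already available (within one month". No QTc value and no action are attached to that tracing.

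The same section gives the only QTc limit in the protocol: "Results of a second EKG done during week 4 will be reviewed to ensure QTc interval is less than 500 msec".

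On timing, Section 6 states: "Participants will receive the study medication during the baseline assessment". Patients are then "instructed to begin the medication on day 1 (1st dialysis day) of week 1 of the study".

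The one cardiac item under Exclusion Criteria is clinical history: "history of myocardial infarction or heart failure within one month of screening or a history of seizures or stroke at any point". Neither the inclusion nor the exclusion list mentions an EKG or QTc. By contrast, the Inclusion Criteria set numeric limits for albumin, phosphate and hemoglobin, and add a rule for patients who miss them: "subjects failing screening due to these blood tests will be allowed to be re-screened in 30 days".

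**The concern.** The protocol treats 500 msec as the value a patient should stay below on treatment, in both arms. It also collects an EKG before treatment, as part of deciding who is eligible. Yet the limit is not applied to that first tracing. A check that first operates in week 4 cannot protect someone who enters already at or above the limit, although the result needed to apply it is available before randomisation.

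What is at stake is patient safety rather than any estimate or test. The population has chronic kidney disease, many may be on dialysis, and the cardiac history exclusion reaches back only one month.

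**Working it through.** The plan gives no figure to reproduce. The check is a reading of every mention of EKG or QTc, followed by calendar arithmetic.

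**Where EKG or QTc appears**

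| Place | What it provides | Limit at entry? |
|---|---|---|
| Section 4, Inclusion and Exclusion Criteria | No mention; cardiac history only | No |
| Section 6, eligibility work-up | EKG obtained unless one from the past month exists | No |
| Section 6, treatment and visits | QTc below 500 msec on the second EKG, week 4 | No, on treatment only |
| Table 1 | EKG marked at week 4 only | No |
| Section 2, choice of drugs | Background statement on bupropion and QTc | No |
| Adverse event collection | Electrocardiograms among chart items to review, if available | No |

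The list under Procedures to Minimize Risks does not fill the gap. It reads "Physical examination and blood test results will be performed reviewed to help detect an increased risk of developing side effects" and does not name the EKG.

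So a patient with a pre-treatment QTc of 500 msec or more fails no written criterion on that account.

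**Time on treatment before the limit applies**

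- First dose: day 1 of week 1.
- Week 4: from day 3 × 7 + 1 = 22 to day 4 × 7 = 28.
- Days of treatment before the day of the week-4 EKG: 22 − 1 = 21 to 28 − 1 = 27.
- Treatment period: 12 × 7 = 84 days.
- Share of the period: 21/84 = 25% to 27/84 = 32%.

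**Doses taken in that time, at the starting schedules**

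- Fluoxetine, or bupropion outside dialysis (daily): 21 to 27 doses. Fluoxetine is at 10 mg/day in week 1 and, as tolerated, 20 mg/day from week 2.
- Bupropion in dialysis patients (two doses a week): 3 × 2 = 6 by the end of week 3, plus 0 to 2 in week 4, giving 6 to 8.

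**With the limit applied at entry**, the time on drug before it first operates falls from 21–27 days to 0.

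**The case against.** The strongest reply is that the first EKG is already an eligibility test. Section 6 lists it among the eligibility assessments and randomises eligible patients; calling the week-4 tracing the second one suggests that the first is also examined. Physicians are involved throughout: study physicians discuss participation with the dialysis physician before the patient starts (Recruitment Process), a study physician takes part in the visits at weeks 1 to 4 (Section 6), and a study physician may withdraw a participant for safety (adverse event section). Several physicians would have to pass over an abnormal tracing for harm to follow.

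This stands as far as it goes: enrolment of such a patient is possible, not certain. But none of these steps carries a QTc trigger, and an EKG reviewed against no stated value is left to individual judgement.

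A second reply is that no drug effect on QTc is shown. Section 2 says bupropion has no clinically significant effect on QTc in patients with MDD, and the fluoxetine risk table lists none. That is fair, and the point here asserts no such effect. The protocol nonetheless requires the week-4 check in both arms, and its own risk table lists abnormal heart rhythm as a less likely serious risk of bupropion. The request is only that the protocol's chosen limit apply when the result is first available.

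Third, the day count measures exposure, not risk, and a 500 msec entry limit would still admit a patient at 499. Both statements are true. A stricter entry value would be a clinical choice that the documents do not inform; 500 msec is the least the protocol's own standard implies.

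Finally, the missing baseline mark in Table 1 is weak evidence, because the physical examination has no row there either. Nothing here depends on it.

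**Conclusion.** The concern holds and should be fixed. The written eligibility rules admit a patient already at or above the limit the protocol sets for patients on treatment, and that limit first operates after about three weeks of dosing. The count assumes that week 4 means days 22 to 28 and that dosing begins on day 1 as instructed; the dose counts assume no change from the starting schedules. The absence of a written entry limit is certain from the text. How many of up to 50 participants it would affect cannot be estimated from the documents.

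**What to change.** Add one line to the Exclusion Criteria: QTc of 500 msec or more on the pre-treatment EKG, with the tracing reviewed before randomisation and before medication is dispensed.

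Two smaller clarifications go with it. State whether the 30-day re-screening allowance for blood tests also covers an EKG failure, and mark the pre-treatment EKG in the baseline column of Table 1 so that the table agrees with the text.

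The cost is one criterion, one sentence and one table mark. The EKG is already performed or retrieved, so nothing is added to the visit. The downside is an occasional extra screen failure.
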